APPENDIX A: PARTICIPANT ELIGIBILITY CHECKLIST

PROTOCOL SYNOPSIS

TITLE	Applying New Device Technologies for Tissue Expander/Implant-Based Breast Reconstruction
	(Blossom Syringe Assist Device)
STUDY PHASE	I
INDICATION	To evaluate a device that has the potential to achieve the same reconstructive goals as conventional tissue expansion in a shorter period of time and while avoiding frequent injections through the skin, which cause patient discomfort and require many clinic visits.
INVESTIGATIONAL PRODUCT OR	Blossom Smart Expander Technology (Syringe
PROCEDURE	Assist Device)
PRIMARY OBJECTIVE(S)	Effectiveness of Blossom Device in 1 st stage of expander to implant breast reconstruction (time to expansion)
SECONDARY OBJECTIVE(S)	Patient satisfaction, self-reported pain, incidence of complications
TREATMENT SUMMARY	Consenting patients will be prospectively enrolled. This investigational device slowly and continuously injects a small amount of saline based on pressure and volume in the expander. The expander devices will be inserted beneath the pectoralis major muscle in the usual fashion immediately after mastectomy. The nature of the surgery remains identical to that for conventional breast tissue expander insertion. Postoperative follow-up with documentation of clinical data will occur on a weekly basis until completion of breast expansion along with stabilization of surgical scars and percutaneous drain removal. Monthly follow-up, as indicated, will occur in preparation for the second stage expander to definitive implant exchange surgery.
SAMPLE SIZE	10

SCHEMA

Patients prospectively enrolled for pilot study. Must meet inclusion and exclusion criteria (please refer to sections 3.1 and 3.2 for specific criteria) n=10

Surgical insertion of Blossom Syringe Assist Device/Mentor SPECTRUM® adjustable saline breast implant for expansion (1st stage of 2-staged implant-based breast reconstruction)

Postoperative follow-up Assessment of primary + secondary outcomes

LIST OF ABBREVIATIONS AND DEFINITION OF TERMS

AE	Adverse event
IBR	Implant-based breast reconstruction
IRB	Institutional Review Board

1. OBJECTIVES

1.1. Primary Objective

The primary objective of this study is to assess the clinical effectiveness of the application of Blossom Smart Expander Technology in 2-staged tissue expander/implant-based breast reconstruction. This new study may lead to the development of a new approach to tissue expander/implant-based breast reconstruction that is better tolerated by patients and decreases the total number of clinic visits. Effectiveness will be measured by total time to expansion, which is the primary outcome being investigated.

1.2. Secondary Objectives

Secondary objectives being investigated include the following:

- Patient Satisfaction
- Patient self-reported pain
- Incidence of complications

2. BACKGROUND

2.1 Study Disease

Tissue expander/implant-based breast reconstruction is the most common form of breast reconstruction in North America following mastectomy in patients diagnosed with either breast cancer or strong genetic predisposition for breast cancer. The conventional breast tissue expander requires weekly-biweekly injections of saline through the skin and into the integrated port using a needle and syringe in order to expand breast skin (standard of care). This is an office procedure and can be uncomfortable for patients, and also results in multiple clinic visits and a time delay (usually several weeks to months) until final expansion volume is achieved. Once this expansion process is complete, the patient may proceed to the 2nd stage surgery where the expander is exchanged for a definitive breast implant, thereby effectively completing reconstruction of the breast mound.

In contrast to the standard of care, the current clinical trial will evaluate the Blossom device as a method to continuously fill the expander with small quantities of saline based on pressure within the chambr and can potentially complete expansion within several weeks without the need for frequent office visits.

2.2 Study Agent/Device/Procedure

Blossom Smart Expander Technology (Syringe Assist Device), currently commercially available, aims to achieve the same reconstructive goals as conventional tissue expansion while avoiding frequent injections through the skin. The Blossom Syringe Assist Device is intended to be used to assist the clinician in the delivery of sterile saline to fill temporary, removable tissue expanders. This device includes a battery powered controller to provide a regulated method for delivery of a specific volume of saline at a specific rate. Supplied with the controller in a kit are the following components: single use sterile 10cc luer lock piston syringe, transfer set with proximal connection to the controller, and saline reservoir including distal connections to the

inflation port of the expander. The fluid path is clear, allowing for visual inspection of the content.

The Blossom device is a tissue expander accessory that allows for slow and continuous injection of small amounts of saline, from an external pouch and based on precise pressure and volume measurements, into breast expander implants.

Blossom Syringe Assist Device is FDA 510K approved. It does not require an Investigational New Drug application (IND).

2.3 Rationale

Weekly or biweekly injections of saline through the skin during conventional tissue expansion result in multiple clinic visits, patient discomfort, and a time delay (usually several weeks to months) until final expansion volume is achieved. The Blossom device may be employed in patients opting for 2-staged implant-based (expander to implant) breast reconstruction, while avoiding the aforementioned drawbacks of serial percutaneous saline injections via automated slow continuous injection based on pressure and volumetric measurements.

2.4 Study Design

- The primary purpose is a protocol designed to evaluate one or more interventions for treating a disease, syndrome, or condition.
- The interventional model is single group
- There is one intervention arm (Blossom Smart Expander Technology [Syringe Assist Device])
- The study will be open (no masking is used).
- The study will not be randomized.
- The primary outcome that the protocol is designed to evaluate is safety/efficacy.

2.5 Correlative Studies Background

There are no planned correlative studies.

3. PARTICIPANT SELECTION AND ENROLLMENT PROCEDURES

Refer to the Participant Eligibility Checklist in Appendix A.

There will be an assessment of how many people are approached and how many people decline or are ineligible, including the reasons for exclusions.

3.1 Inclusion Criteria

3.1.1 Diagnosis of breast cancer or reason for prophylactic mastectomy (e.g., BRCA mutation and/or strong family history of breast cancer), both unilateral or bilateral mastectomy.

- 3.1.2 No prior breast surgery (excluding biopsy and lumpectomy) or breast radiation.
- 3.1.3 Women age 18 years or older, no race-ethnic restrictions.
- 3.1.4 Ability to understand and the willingness to sign a written informed consent document.
- 3.1.5 No life expectancy restrictions.
- 3.1.6 ECOG or Karnofsky Performance Status will not be employed.
- 3.1.7 No requirements for organ and marrow function.

3.2 Exclusion Criteria

- 3.2.1 Recent steroid use.
- 3.2.2 No major medical comorbidities (defined as ASA III or greater⁶)
- 3.2.3 No connective tissue disorder
- 3.2.4 Prior breast surgery, excluding biopsy and lumpectomy
- 3.2.5 History of or plan for breast radiation
- 3.2.6 Pregnancy and nursing patients will be excluded from the study
- 3.2.7 No restrictions regarding use of other Investigational Agents.
- 3.2.8 No exclusion criteria related to history of allergic reactions.
- 3.2.9 No exclusion criteria relating to concomitant medications or substances that have the potential to affect the activity or pharmacokinetics of the study agent, except as per 3.2.1.
- 3.2.10 No other agent-specific exclusion criteria.
- 3.2.11 No exclusion of cancer survivors or those who are HIV-positive.

3.3 Informed Consent Process

All participants must be provided a consent form describing the study with sufficient information for participants to make an informed decision regarding their participation. Participants must sign the IRB approved informed consent prior to participation in any study specific procedure. The participant must receive a copy of the signed and dated consent document. The original signed copy of the consent document must be retained in the medical record or research file.

3.4 Randomization Procedures

N/A

3.5 Study Timeline

Primary Completion:

The study will reach primary completion 12 months from the time the study opens to accrual.

Study Completion:

The study will reach study completion 24 months from the time the study opens to accrual.

4. TREATMENT PLAN

All consenting patients presenting to [name] breast reconstruction clinic and opting for immediate 2-staged tissue expander/implant-based breast reconstruction after

mastectomy will be given the option of study enrollment. Consenting patients will be prospectively enrolled to undergo 2-staged IBR with the application Blossom Smart Expander Technology (Syringe Assist Device) in the first stage (tissue expansion). The Mentor Spectrum saline implant (FDA approved device) is placed in the mastectomy skin pocket at the time of reconstruction. The fill tube is externalized and connected to the Blossom Syringe Assist Device that controls the gradual continuous fill of the Mentor Spectrum based on the pressure within the mastectomy skin pocket. The Mentor Spectrum implant stays in the patient for the duration of the expansion, approximately 2-3 weeks. The Blossom device is external and is detachable. BlossomTM Instructions for Use that a saline bag of no greater than 250cc be connected to the transfer set. If required, additional saline bags can be attached. There are 3 rates of infusion that can be selected by the physician to achieve optimal results. The volume delievered is determined by the difference in the initial and remaining volume in the saline bag. The nature of the surgery remains identical to that employed for conventional breast tissue expander insertion following mastectomy. The Blossom device is connected at the time of surgery. The decision to initiate filling immediately intraoperative versus in the clinic is determined by the surgeon based on conition of the patient's skin. This decision making process is similarly being done currently with conventional tissue expander reconstruction. This device can be used in immediate or delayed reconstruction. The pressue sensing technology and the ability to infuse very small quantity of liquid continuously offer a key advantage over conventional TE approach to allow patients with immediate TE reconstruction to complete their expansion earlier and safely. Postoperative follow-up will occur within 1 week of surgery. Weekly follow-ups with documentation of clinical data throughout will also take place until completion of the expansion, stabilization of surgical scars, and removal of all percutaneous drains. Thereafter, follow-ups will be scheduled as needed (monthly) according to usual clinical practice in implant-based breast reconstruction in preparation for the second stage expander to definitive implant exchange. Time to expansion completion, patient satisfaction (including self-reported pain), and incidence of complications will be recorded throughout the follow-up period.

A video recording of 1-2 cases in the study group may occur (intraoperative). The purpose of these videos would be to demonstrate the placement of the Blossom Smart Expander Technology in-situ. These recordings may also supplement eventual publications and scientific presentations. Only patients specifically consenting to video recording will be affected. All videos will be deidentified (no facial identification possible). Videos will be kept in a secure, encrypted location and destroyed within 5 years following completion of the study. Photography will be routinely used pre- and postoperatively, with appropriate patient consent, in order to document aesthetic outcomes. Tissue samples will not be retained for future research.

4.1 General Concomitant Medication and Supportive Care Guidelines

The Women's Cancer Center is a collaborative environment for treatment of women with breast disease. Physicians remain apprised of other protocols in which their patients are involved through direct communication with other physicians and review of patients' electronic medical record. Patients in our study will not be routinely involved in more than one study, though this would not preclude study participation. There will be no routine use of concomitant medications or any additional supportive care medications or treatments. Concomitant radiotherapy is an exclusion criterion for study participation.

Procedures performed are a normal part of clinical management for this condition. Risks associated with the Blossom device include device malfunction. Risks also include those common to all tissue expanders used in conventional tissue expansion (standard of care): infection, extrusion, and pain. Importantly, in the event of any pain due to volume fill, the Blossom technology device can easily be disconnected by the patient in a reliable and safe manner.

The care of the port is much like drain care. The patient will have a demonstration of the Blossom Device and how to clean the port by the Nurse Coordinator at the time of pre-op. This will be reinforced post-op and in clinic much like conventional tissue expander reconstruction. The patient will also receive written patient instructions.

4.2 Criteria for Removal from Study

Patients will be removed from the study in the event of withdrawal of consent. Patients would then be eligible for placement of conventional tissue expanders. The study as a whole would only be terminated prematurely if the Blossom device proved to be clearly more ineffective, since traditional tissue expansion is still a safe and effective method of expansion. The study will terminate if there is increased incidence of complications noted above rates of complications reported in the standard tissue expander-implant reconstruction.

4.3 Alternatives

Patients will be monitored at routine clinic follow-up visits. They are counseled on warning signs that should prompt a call to their physician, and provided with a phone number at which they can reach a physician for advice at all hours. None of these methods of protection jeopardizes patient confidentiality beyond the risks inherent in routine patient care. A study participant selected for the Blossom Smart Expander Technology tissue expander/implant-based breast reconstruction arm may undergo the alternative, conventional tissue expander/implant-based breast

reconstruction, only if she chooses to withdraw from the study. There are no other alternatives available within the study.

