The Blossom Syringe Assist Device is intended to be used to assist the clinician in the delivery of sterile saline to fill temporary, removable tissue expanders. This device includes a battery powered controller to provide a regulated method for delivery of a specific volume of saline at a specific rate. Supplied with the controller in a kit are the following components: single use sterile 10cc luer lock piston syringe, transfer set with proximal connection to the controller, and saline reservoir including distal connections to the inflation port of the expander. The controller (pump) is 6.5" long, 3.5" tall, 1.25" wide and weighs 0.7lbs. AA batteries are changed every 3 days. There is a low battery indicator to remind patients to change the AA batteries every 3 days. The fluid path is clear, allowing for visual inspection of the content. If the device fails and a manual process is used. The device can be detached from the fill tube. The fill tube of the Mentor Spectrum device is externalized much like a drain and connected to the Blossom Syringe Assisted Device. It is expected to have the similar rate of infection as a standard drain.

A Mentor Spectrum® adjustable saline breast implant for expansion, coupled with the Blossom Syringe Assist device, will be inserted beneath the pectoralis major muscle in the usual fashion immediately after mastectomy. The nature of the surgery remains identical to that employed for conventional breast tissue expander insertion following mastectomy.

Please see attached instruction brochure for further information on Blossom Technology.

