5.4 Agent Accountability

The Blossom devices/kits will be stored together with the appropriate ordered breast implants for each individual patient.

6. **DOSE MODIFICATIONS**

No treatment modifications are envisioned.

If the investigational device were to fail to achieve the projected expansion of the breast skin, conversion to the traditional breast expander device with manual percutanous saline injections would be carried out, as indicated.

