10. MEASUREMENTS

10.1 Primary outcome measure: time to full expansion

- 10.1.1 This outcome will be measured on all subjects.
- 10.1.2 Defined as number of days until desired expansion volume is achieved. This outcome is not assessing a safety issue.
- 10.1.3 Outcome will be measured by calculating the number of days from expander placement to achievement of desired expansion volume.
- 10.1.4 Measurement time points include date of expander placement and date that desired expansion volume is reached. Follow-up will be 12 months.
- 10.1.5 Response is not the primary outcome.

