12.4.1 Analysis Population

All participants will be included in this analysis. Primary analysis will be an intent-to-treat principle.

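### Section 4.3 ties conventional expansion to leaving the study while section 6 provides for conversion with no mention of withdrawal, and the plan does not say how converted patients are followed or counted

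*Combined protocol and SAP*

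**What the plan says.** Four places deal with a patient who stops using the device or moves off it.

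- Section 4.3 makes conventional expander-based treatment available under this condition: "reconstruction, only if she chooses to withdraw from the study. There are no other alternatives available within the study".
- Section 4.2 gives the matching removal rule: "Patients will be removed from the study in the event of withdrawal of consent. Patients would then be eligible for placement of conventional tissue expanders". It states no other ground for removing a patient.
- Section 6 has its own trigger, "If the investigational device were to fail to achieve the projected expansion of the breast skin", and its own action, "conversion to the traditional breast expander device with manual percutanous saline injections would be carried out, as indicated". It does not mention withdrawal.
- Section 5.1 describes a device failure in a sentence that is grammatically incomplete: "If the device fails and a manual process is used. The device can be detached from the fill tube". It mentions neither a new expander nor withdrawal.

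Sections 4.1 and 7.1 add that "in the event of any pain due to volume fill, the Blossom technology device can easily be disconnected by the patient", without saying what follows.

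On the analysis side, 10.1.1 requires the primary outcome on every subject, and 10.1.3 defines it: "Outcome will be measured by calculating the number of days from expander placement to achievement of desired expansion volume". Section 12.4.1 reads: "All participants will be included in this analysis. Primary analysis will be an intent-to-treat principle". The test is a t-test against literature values (12.4.2). Section 12.7 makes a faster time at p<.05 one of the criteria for a larger trial. The only sentence on missing data is in 12.5.1 and concerns the secondary analyses.

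**The concern.** The restriction in 4.3 makes no exception for a device that fails to expand the breast, so it cannot stand beside the conversion in section 6. A site with such a patient can find support for two different study statuses: withdrawn, or still a participant.

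This matters because the reason for converting is poor device performance. If the patient withdraws and nothing more is recorded, the primary outcome is missing for exactly the patients with the longest times, and the mean of the rest is too short. Complications found later may also go unrecorded. Time to expansion and complications both feed the criteria in 12.7, and complications also feed the study-termination rule in 4.2.

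A second, smaller gap concerns the clock. After a section 6 conversion there are two expander placements, and 10.1.3 does not say which one starts the count.

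**Working it through.** **Side by side.** The real conflict is between 4.3 (with 4.2) and section 6. Section 5.1 can be read as manual filling of the same implant after the controller is detached. On that reading it does not conflict with 4.3, but its wording needs clarifying. The resulting data would be:

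- 4.2/4.3 route: the patient leaves, and no text provides for assessment afterwards.
- Section 6 route: the patient is not said to leave; there are two placement dates.
- Section 5.1 route: the patient is not said to leave; there is one placement date.

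**Size.** The plan gives no SD, conversion rate, conversion time or power calculation, so there is no figure of its own to reproduce. What follows is an illustration.

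Inputs from the documents:
- Sample size 10 (12.6.1).
- Comparator 6.6 weeks (12.6.3): 6.6 × 7 = 46.2 days.
- Expected duration of expansion about 2-3 weeks (section 4).

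Assumed inputs:
- Three converts: the other seven finish on Blossom at 14, 15, 16, 18, 20, 21 and 22 days (sum 126).
- Two converts: the other eight finish at 14, 15, 16, 17, 18, 20, 21 and 21 days (sum 142).
- Each convert changes at day 21 and needs 46 more days: 21 + 46 = day 67 from first placement, or 46 days if the clock restarts.

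Test: t = (mean − 46.2) / (SD/√n), with n − 1 degrees of freedom, two-sided unless stated.

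| Case | n | Mean (days) | SD | t | p |
|---|---|---|---|---|---|
| 2 converts, dropped | 8 | 142/8 = 17.75 | 2.7 | −29.7 | <0.001 |
| 2 converts, first placement | 10 | (142 + 134)/10 = 27.6 | 20.9 | −2.81 | 0.020 |
| 3 converts, dropped | 7 | 126/7 = 18.0 | 3.1 | −24.0 | <0.001 |
| 3 converts, clock restarted | 10 | (126 + 138)/10 = 26.4 | 13.8 | −4.55 | 0.0014 |
| 3 converts, first placement | 10 | (126 + 201)/10 = 32.7 | 23.8 | −1.79 | 0.107 (one-sided 0.053) |

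Dropping the converts therefore shortens the mean by 27.6 − 17.75 = 9.85 days with two, and by 32.7 − 18.0 = 14.7 days with three.

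**Sensitivity.** If the three converts finish at day 61, the mean is (126 + 183)/10 = 30.9 days, t = −2.31 and two-sided p=0.046. If they finish at day 66, one-sided p=0.047.

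A second set of assumptions gives the same pattern: Blossom completers centred on 17.5 days with SD 3, 5 or 8, and converts finishing at 21 + 46.2 = 67.2 days from first placement. The two-sided p-values, in order of SD, are 0.020, 0.022 and 0.025 with two converts, and 0.104, 0.107 and 0.114 with three. With one convert, p is at most 0.002.

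**The case against.** The strongest reply is that the sections have different triggers. Section 4.3 concerns a patient who chooses another method, 5.1 a device that fails, and section 6 a device that does not reach the projected expansion. Nothing says that a converted patient is removed; withdrawal of consent is the only stated ground. Sections 10.1.1, 12.4.1 and 12.5.1 all call for every participant, and 10.1.4 refers to a single placement date, so under intent-to-treat the first placement is the natural start.

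Much of this stands. Loss of data is an inference that holds only on the 4.2/4.3 route, and a restarted clock is a strained reading. What does not stand is that different triggers remove the conflict: the restriction in 4.3 has no exception for failure.

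A reader might infer three stronger points that the documents do not support:

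- *That stopping the device and leaving the study are the same act.* Section 4.3 restricts access to conventional treatment, not stopping Blossom; 4.1, 5.1 and 7.1 allow disconnection or detachment without withdrawal.
- *That a conversion for slow expansion would appear in no outcome.* The complications in 10.3.2 are introduced as an open list, and slow expansion would show in the primary outcome if the patient is followed. Conversion is simply not named.
- *That one complication in ten patients would become none in nine.* Section 12.5.1 keeps all participants in the secondary analyses and reports missing data as such, so the denominator stays ten. Section 7.2 also tracks serious events for a period after treatment.

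**Conclusion.** The concern holds in limited form. Section 4.3, with 4.2, conflicts with section 6 on whether a patient can move to conventional expansion and remain a participant. The plan does not state study status, follow-up or counting for such patients. If the 4.2/4.3 route is followed, the likely result is a mean time biased towards faster, contrary to 10.1.1 and 12.4.1.

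Under the assumed data the shift is about 10 days with two converts of ten and about 15 with three. The main damage is to the estimated mean. A reader might infer that the p<.05 criterion in 12.7 is itself unsafe. The illustration supports that only with about three or more converts and late completion: two converts leave p=0.020, and three finishing at day 61 rather than 67 return p to 0.046. Section 12.7 does not state whether the test is one- or two-sided, and no document supplies a conversion rate.

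For a ten-patient single-arm pilot, this should be corrected but is not a fault that invalidates the study.

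**What to change.** Reconcile 4.2, 4.3 and 6, and clarify the incomplete sentence in 5.1, on what happens when the device is stopped or fails. The clinical route is for the sponsor to settle. Whatever the route:

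1. State that stopping or converting the device is not in itself withdrawal of consent to data collection.
2. Keep these patients in the scheduled assessments and in the 12.4.1 and 12.5.1 populations unless they withdraw consent to follow-up.
3. In 10.1.3, count days from the first expander placement, including time on manual or conventional filling.
4. Report how many patients reached the desired volume on Blossom alone and how many converted.

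The cost is an amendment of a few sentences and two CRF fields: the date and reason for stopping the device, and the filling method afterwards. No extra study visits are needed if these patients follow the existing schedule. The downside for the sponsor is that the reported mean time may be less favourable.
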